Selection of the margin is a critical component of a non-inferiority trial. Here, we specify a margin of 1 g/dL for haemoglobin levels at 4 months. Under a collection of reasonable assumptions, this margin will ensure that the majority of those with low haemoglobin at baseline will have haemoglobin levels at 4 months above the threshold for anaemia and should therefore qualify as donors. To see this, assume that half of donors are anaemic at baseline (using the thresholds for anaemia of 13 g/dL for men and 11.5 g/dL for women). A simple calculation finds that if we assume haemoglobin levels are normally distributed (which is a reasonable assumption based on observed distributions for haemoglobin in healthy individuals) and the standard deviation of baseline haemoglobin levels is 1.89 g/dL (this estimate will be described below) then the mean haemoglobin level among men who are deferred is 11.5 g/dL and the mean haemoglobin level among men who are not deferred is 14.5 g/dL (these values for women are 10.0 g/dL and 13.0 g/dL). If we assume that the haemoglobin level among those who are not deferred is the same 4 months later then a margin of 1 g/dL implies a mean haemoglobin level among those with anaemia at baseline of at least 13.5 g/dL for men and 12.0 g/dL for women. Thus, the mean haemoglobin level after 4 months of iron supplementation among those who should have been deferred will exceed the threshold for anaemia and consequently, if the distribution of haemoglobin levels is symmetric, the majority of those who were anaemic at baseline would qualify as donors (in fact at least 60.4% would pass the threshold for both sexes if this distribution is normal). Note that the threshold for the copper sulphate test used for women is 12 g/dL, not 11.5 g/dL, so under these assumptions 50% of women would pass the copper sulphate test. Nonetheless, since well over 50% of donors are men the majority of deferred donors would pass the copper sulphate test. It is

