Individuals in blood donor groups will proceed with routine assessment by blood donation staff for eligibility for whole blood donation as defined by the NBSG. As part of this assessment, these potential blood donors will undergo routine semi-quantitative haemoglobin assessment using the copper sulphate (CuSO_4) gravimetric method with a cut- off Hb concentration value of <13.0 g/dL for males and <12.0 g/dL for females. Prospective blood donors who consent and meet the eligibility criteria will be eligible for the study. The site will log potential blood donors who are approached to participate in the study and document whether the participant elects or declines involvement with the study.

- *Consenting Procedure*

Prospective blood donors who pass all pre-donation assessments, and those who are deferred specifically on account of failed CuSO_4 will be approached and informed about the study by trained research assistants. All eligible participants will provide written informed consent and, in the case of minors, additional assent. Eligible enrolled minors who turn 18 during the course of the study will need to be re-consented as adults.

- *Rescreening*

Rescreening will be allowed for previously excluded participants after four months. In this case a new study identification number will be assigned to the participant and the participant will be identified with this new number for the rest of his/her participation in the study. If participant has been enrolled, re-screening is not allowed. In case rescreening occurs, all evaluations re-assessed should meet the eligibility criteria. A new informed consent form (ICF) must be signed only if there is an interruption in the participant's eligibility evaluation and the investigator chooses to re-screen the participant following screen failure. If a new ICF is signed,

AEs and medical history will be assessed relative to the new informed consent date.

- *Blood Sampling:*

Participants who consent/assent to participate will have 5ml of whole blood sampled into an EDTA tube for full blood count, peripheral film comment, malaria rapid test and plasma ferritin analysis. This blood draw will take place prior to donation for those participants who can donate to prevent a classification of ID due to sampling immediately after a donation.

- *Estimation of Iron Deficiency and Iron Deficiency Anaemia*

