Anaemia is a state in which the amount of red blood cells (RBCs) is insufficient to meet the body's physiologic needs ²⁴. Mild anaemia is defined as Hb ranging from 11-12.9 g/dL in adult males and 11-11.9 g/dL in adult females. Moderate anaemia is defined as Hb level of 8-10.9 g/dL and severe anaemia is defined as Hb level of less than 8 g/dL for all the age groups ^{25,26}.

Following FBC and plasma ferritin estimation, screened participants will be classified by the WHO criteria as shown in Table 4:

Table 4: Definition of Iron Status Criteria

| Haemoglobin concentration, g/dL | Plasma ferritin concentration µg/L | Interpretation |
|--|------------------------------------|---|
| [Male] >13.0 [Female] >11.5 | < 15 | Iron deficiency without anaemia |
| [Male] ≥8.0-13.0 [Female] ≥8.0-11.5 | < 15 | Iron deficiency with mild to moderate anaemia |

| | | | |
|-------|------|------|-------------------------------------|
| [All] | <8.0 | < 15 | Iron deficiency with severe anaemia |
|-------|------|------|-------------------------------------|

Schedule of Assessments (Table 5)

| Assessment | Screening (Day -14 to 0) | Enrolment (Day 0) | Biweekly (Throughout) | Interim Visit 1 | Interim Visit (Week 8-10) | Interim Visit 2 | Final Visit (Week 24) |
|--|-----------------------------|----------------------|--------------------------|--------------------|------------------------------|--------------------|--------------------------|
| NBSG Pre-Donation Assessment | X | | | | | | X |
| Informed Consent | X | | | | | | |
| Inclusion and Exclusion Criteria | X | | | | | | |
| Demographics | X | | | | | | |
| Full Blood Count and peripheral blood comment | X | | | X | X | X | |
| Plasma Ferritin | X | | | X | X | X | |
| Malaria Parasites Testing (RDT) | X | X | | X | X | X | |
| Nutritional Counselling | | X | | X | X | X | |
| Qualitative Assessment | | | | | | | X |
| Follow-Up Calls | | | X | | | | |
| Return Blood Donation Status | | | | X | X | X | X |
| Assessment for Adverse Events | | X | X | X | X | X | X |
| Adherence Assessment (for those receiving supplemental iron) | | | X | X | X | X | X |
| RDT – Rapid Diagnostic Test | | | | | | | |

Enrolment

Participants will be re-assessed with their laboratory results at the Day 0 visit.

- ***Eligibility Check***

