Analytical approaches to the analysis of data from the prevalence study will focus on univariate summaries but will also investigate risk factors for deferral, ID, and IDA. Exact confidence intervals for the probability of deferral, the probability of ID and the probability of IDA will be computed using the method first described by Clopper and Pearson. Logistic regression will be used to assess risk factors for these outcomes. For deferral, these risk factors will include age and sex but likely little else as the data we can obtain for these individuals is limited. For ID and IDA, the role of demographics will be investigated as well as other factors including socio-economic status, medical history, and diet. Final models for the impact of risk factors on deferral, ID, and IDA will include demographics and a selection of covariates found to have a statistically significant univariate association with each of these outcomes.

The analysis for the primary outcome of haemoglobin levels at 4 months will be conducted using a linear model with haemoglobin levels at 4 months as the response variable. It is unlikely that there is a need to transform the response variable as haemoglobin levels are usually symmetrically distributed with tails that decay at rates consistent with the normal distribution. However, if informal univariate assessments of normality (e.g., qq-plots) indicate strong departures from these expectations, the Box-Cox transformation will be used to select a transformation. The set of explanatory variables will be group membership (i.e.,

received iron supplementation or not), baseline haemoglobin, sex, and age. A 1-sided t-test for the regression coefficient associated with group membership will be conducted with a significance level of 0.025 to test the inferiority hypothesis. This analysis will exclude individuals who did not receive iron supplementation at baseline but received it during follow-up due to changes in ferritin or haemoglobin values. The frequency of this will be closely tracked and if more than 10% of participants in the group initially not receiving iron supplementation receive iron supplementation during follow-up, alternative analysis approaches will be considered and presented to the DSMB. At a minimum, sensitivity analyses which include those requiring iron supplementation during follow-up will be pursued. These analyses will include those requiring supplementation during follow-up in each of the 2 groups.

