### **Secondary Objectives**

- To determine changes in haemoglobin in blood donors over a 6-month period.
- To determine the impact of iron supplementation on the change in haemoglobin.
- To estimate the prevalence of ID and IDA in prospective first-time blood donors.
- To determine the factors associated with ID and IDA among prospective blood donors.
- To determine the prevalence of malaria or adverse events among the prospective first-time blood donors.
- To identify the barriers and facilitators of repeat donation and the use of dietary and iron supplementation interventions to address ID and/or anaemia among blood donors.
- To determine feasibility of the intervention, through documenting implementation fidelity, intervention adaptation, and intervention strengths and weaknesses.
- To understand participant and key informant acceptance of the intervention.
- To develop and implement key strategies aimed at increasing the blood donor pool.

- To compare haemoglobin levels as determined by copper sulphate versus automated haematology analyser.

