## **7 Quantitative Data Analysis**

### **7.1 Cross-sectional study**

Analytical approaches to the analysis of data from the prevalence study will focus on univariate summaries but will also investigate risk factors for deferral. An exact

confidence interval for the probability of deferral will be computed using the method first described by Clopper and Pearson. Logistic regression will be used to assess risk factors for deferral. These risk factors will include age, sex, previous donation status and type of donor.

Since recruitment at donation events focuses on informing individuals who fail the copper sulphate test about the study, we expect that the proportions of those who are ID and IDA will be higher than the proportion among those attending a donation event. For this reason, we will estimate the level of ID and IDA overall by weighting the estimates within deferral strata by the observed probability of deferral based on the cross-sectional study of deferral (but restricted to first time donors, or voluntary first time donors depending on who enrolls into the ID/IDA study). To obtain 95% confidence intervals for the overall proportion of those who are ID and IDA we will use a Bayesian approach in which we sample the probability that first-time donors are deferred for low haemoglobin from its posterior distribution (which is a beta distribution) and we sample the probability of being ID and IDA conditional on deferral status from their posterior distributions (which will also be beta distributions). We can then combine these draws from the posterior distributions to obtain weighted estimates of the probability of being ID and IDA that will be consistent for these probabilities in the overall population. Risk factors for being ID and IDA conditional on the outcome of the copper sulphate test will be examined using logistic regression.

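### SAP 7.1 models ID and IDA risk factors only conditional on the copper sulphate result, so the odds ratios do not describe prospective donors and non-iron causes of low haemoglobin tend to look protective

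*SAP*

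**What the plan says.** The secondary objective is "To determine the factors associated with ID and IDA among prospective blood donors" (SAP 1.2, Secondary Objectives). It carries no restriction by test result.

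The protocol (Quantitative Data Analysis) plans ordinary models: "Logistic regression will be used to assess risk factors for these outcomes". For ID and IDA, "the role of demographics will be investigated as well as other factors including socio-economic status, medical history, and diet".

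The SAP changes this because donors who fail the copper sulphate test are over-recruited (SAP 1.2, Stratification and Sampling). SAP 7.1 deals with the over-recruitment in two ways. Prevalence of ID and IDA is weighted back to the donor population using the observed deferral probability. Risk factors are handled differently: "Risk factors for being ID and IDA conditional on the outcome of the copper sulphate test will be examined using logistic regression". The SAP does not say whether this means a covariate or separate strata, and it plans no weighted or unconditional risk-factor model.

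The test fails a donor at an "Hb concentration value of <13.0 g/dL for males and <12.0 g/dL for females" (Protocol, Donor Eligibility Screening). The margin argument in the protocol's Design section works "using the thresholds for anaemia of 13 g/dL for men and 11.5 g/dL for women". Protocol Table 4 uses the same haemoglobin limits, with ferritin below 15 µg/L, for the category "Iron deficiency with mild to moderate anaemia".

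**The concern.** The protocol's Introduction describes anaemia as a later stage of untreated ID, so the copper sulphate result lies downstream of ID. In men its cut-off is also the haemoglobin limit for IDA. Conditioning on it therefore means conditioning on an effect of one outcome and on nearly half the definition of the other.

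Two consequences follow.

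- Among donors who fail, low haemoglobin has to come from somewhere. A factor that lowers haemoglobin without touching iron competes with ID as the explanation, so it appears negatively associated with ID even when the two are unrelated among donors.
- Women fail below 12.0 g/dL but are anaemic only at 11.5 g/dL or less. Female failures include some non-anaemic women, while male failures include almost no non-anaemic men. That alone shrinks the association of sex with IDA.

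At stake is how the risk-factor results are read. A factor that raises the risk of IDA among donors could be reported as neutral or protective. Sex, malaria and blood film abnormalities are all recorded for the whole ID/IDA study (SAP 3.4), and malaria excludes people from the trial only (SAP 3.1).

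**Working it through.** **1. The plan's own figures.** The documents give no odds ratio, power or precision for these models, only the sample size. It reproduces: 2 × 1.89² × (1.960 + 1.036)² / (1.0 − 0.3)² = 130.9, so 131 per arm; 262 / 0.9 = 291.1, so 292. The problem is the choice of model, not the size.

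**2. Thresholds side by side (g/dL).**

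| | Fails copper sulphate | Anaemic (part of IDA) | Gap |
|---|---|---|---|
| Men | below 13.0 | 13.0 or less | 0 |
| Women | below 12.0 | 11.5 or less | 0.5 |

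With an error-free test nobody who passes has IDA. With test error SD 0.5 to 1.0 (assumed), about 2-7% of men who pass have IDA. If 146 of the 292 are passes, that is about 0 to 10 cases. The IDA model is then essentially a comparison within failures.

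**3. Assumptions (not in the documents).** 25% women; ID in 30% of men and 50% of women; mean haemoglobin without ID 14.2 (men) and 12.7 (women); ID lowers it by 1.5; SD 1.6 within sex and ID status.

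- Overall mean: men 14.2 − 0.30 × 1.5 = 13.75; women 12.7 − 0.50 × 1.5 = 11.95; 0.75 × 13.75 + 0.25 × 11.95 = 13.3.
- Overall variance: 1.6² + (0.75 × 0.21 + 0.25 × 0.25) × 1.5² + 0.75 × 0.25 × 1.8² = 2.56 + 0.495 + 0.6075 = 3.66, so the SD is 1.91.

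The documents give 13.4 and 1.89 (SAP 2.4), so the set is close to them.

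**4. ID: factor X, unrelated to iron, lowers haemoglobin by c (men).** Let f(i,x) be the probability of failing given ID = i and X = x. By Bayes' rule:

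OR among failures = population OR × [f(1,1)/f(0,1)] / [f(1,0)/f(0,0)]

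Without test error:

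- f(0,0) = Φ(−1.2/1.6) = 0.2266; f(1,0) = Φ(0.3/1.6) = 0.5744; ratio 2.535.
- c = 0.5: 0.6915/0.3309 = 2.090; 2.090/2.535 = **0.82**.
- c = 1.0: 0.7917/0.4503 = 1.758; 1.758/2.535 = **0.69**.
- c = 0: the ratios cancel and the factor is **1.00**. A factor acting only through iron keeps its ID OR.

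The true OR is 1.0 throughout. Test error SD 0.4 replaces 1.6 by √(1.6² + 0.4²) = 1.649 and gives 0.83 and 0.71.

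**5. IDA: the same factor (men).**

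- Population, X = 0: 0.30 × 0.5744 = 0.1723, odds 0.2082.
- c = 0.5: 0.30 × 0.6915 = 0.2074, odds 0.2617, OR **1.26**.
- c = 1.0: 0.30 × 0.7917 = 0.2375, odds 0.3115, OR **1.50**.

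With an error-free test every failing man with ID has IDA, so the OR among failures equals that in step 4: 0.82 and 0.69. Test error softens this (step 7).

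**6. IDA: female sex.**

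- Population: women 0.50 × Φ(0.3/1.6) = 0.2872, men 0.1723; OR = (0.2872/0.7128)/(0.1723/0.8277) = **1.94**.
- Failing men: 0.70 × 0.2266 + 0.1723 = 0.3309; IDA odds among them 0.1723/0.1586 = 1.086.
- Failing women (12.0): 0.50 × 0.3309 + 0.50 × 0.6915 = 0.5112; IDA odds 0.2872/0.2240 = 1.282.
- OR among failures: 1.282/1.086 = **1.18**.

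If women failed at 11.5 the OR would be (0.2872/0.1133)/1.086 = 2.33. The 0.5 g/dL gap therefore produces the attenuation here. With SD 1.1 instead of 1.6 the OR among failures is (0.3037/0.2106)/(0.1822/0.0964) = 0.76, but the overall SD is then only √(1.21 + 0.495 + 0.6075) = 1.52.

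**7. Both sexes, test error, half the sample from each stratum.** Simulation at an overall SD near 1.89, with c = 0.5 to 1.0, gave an ID OR of 1.0 becoming 0.84 to 0.72; an IDA OR of 1.31-1.64 becoming 0.93-0.87; and a female-sex IDA OR of about 1.8 becoming 1.2-1.4. A second run (SD 1.6 within sex, test error SD 0.4) gave 0.85 to 0.71 for ID, and 1.28-1.53 becoming 0.92-0.82 for IDA.

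**8. When the sign changes for ID.** With larger non-iron effects (1 to 2 g/dL, SD 1.89), a true ID OR of 1.2 became 0.52-0.98. A true ID OR of 2.0 with a 1 g/dL effect became 1.23-1.63, which is attenuated only.

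**9. The repair.** Weighting each stratum back to its share of donors, without the copper sulphate term, returned the population OR in every setting. Dropping the term without weights did not: in one setting an IDA OR of 1.52 came out as 1.74.

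**The case against.** Conditioning is a deliberate and openly stated answer to a real problem. Sampling depends on the test result, so the analysis must either condition on it or weight for it. Within-stratum odds ratios are valid descriptions of donors who fail and donors who pass, and the objective speaks of association, not cause. Many candidates, such as diet and blood loss, plausibly act mainly through iron. Participants are screened and healthy, so a non-iron effect of 0.5 to 1.0 g/dL may be uncommon. Precision is low too: with 292 participants, 45% ID (assumed) and a factor present in 20-50%, the 95% interval for an OR reaches a factor of about 1.6 to 1.8 either way. Spurious ORs of 0.7 to 0.85 sit inside that.

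Much of this stands. It limits the severity, makes every size above illustrative, and justifies keeping the stratum-specific models as description. It does not rescue them as the answer to the objective. Association among prospective donors is a different quantity from association given the test result, whether or not it is read causally. SAP 7.1 accepts that distinction for prevalence and weights for it. The analyst also cannot know beforehand which factors act only through iron, and imprecision does not excuse a systematic shift in a known direction.

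**Conclusion.** The point holds as a should-fix. The only risk-factor analysis in the SAP for this secondary objective estimates something other than what the objective asks for. The direction follows from the documents' own thresholds and their description of anaemia as a later stage of ID. The sizes rest on the assumptions in the working, chosen to lie near the documents' mean and SD: an ID OR of 1.0 becomes about 0.85 to 0.7, an IDA OR of about 1.3-1.6 becomes about 0.9, and the female-sex IDA OR falls from about 1.8 to 1.2-1.4.

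Three stronger readings are tempting and not supported.

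- A reader might infer that every odds ratio is distorted. A factor acting only through iron keeps its ID OR exactly.
- A reader might infer that the sex association reverses. Near the documents' SD it is attenuated; it falls to or below 1 only with a clearly smaller SD.
- A reader might infer that the trial or the cross-sectional study is compromised. The primary outcome does not use these models, and prevalence is already weighted. This is one of several secondary objectives in a pilot.

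**What to change.** In SAP 7.1, replace the sentence on risk factors with text to this effect: the main analysis of risk factors for ID and for IDA is a logistic regression without the copper sulphate result. Each participant is weighted by the inverse sampling fraction of his or her copper sulphate stratum, that is, the number of donors in the stratum in the deferral study divided by the number sampled into the ID/IDA study. The deferral-study count is restricted to the same first-time (or voluntary first-time) donors already used for the prevalence weights.

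The standard errors should allow for the weights being estimated, for example by a bootstrap that also resamples the deferral data, or by carrying through the posterior draws already planned for prevalence. SAP 2.4 already recognises this source of variability for the post-stratified prevalence.

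Report the models conditional on copper sulphate as descriptive only, and say whether they use a covariate or separate strata.

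The cost is a short SAP edit and somewhat wider intervals from unequal weights. No new data are needed. The weights rely on participants being representative within each stratum, which the SAP already assumes for prevalence.

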## 7.2 Parallel group trial

**Analysis cohort:** The intervention group is the group assigned oral iron supplementation at enrolment and the control group consists of those not assigned oral iron supplementation at enrolment.

